5.1 Inclusion Criteria

Participants are eligible to be included in the study only if all the following criteria are met:

1. Clinical or mutational diagnosis of TSC consistent with ([Northrup et al, 2021](#)):
 - a. Molecular confirmation of a pathogenic mutation in *TSC1* or *TSC2*. A pathogenic mutation is defined as a mutation that clearly prevents protein synthesis and/or inactivates the function of the *TSC1* or *TSC2* proteins (eg, nonsense mutation or frameshift mutations, large genomic deletions) or is a missense mutation whose effect on protein function has been established by functional assessment. The principal investigator (PI) or designee must review the results of the [REDACTED] and confirm that the causal relationship to the epilepsy syndrome is likely.

OR

1. Clinical diagnosis of definite TSC which includes 2 major features or 1 major feature with ≥ 2 minor features.

Major features	Minor features
Hypomelanotic macules (≥ 3 , at least 5-mm diameter)	“Confetti” skin lesions
Angiofibroma (≥ 3) or fibrous cephalic plaque	Dental enamel pits (≥ 3)
Ungual fibromas (≥ 2)	Intraoral fibromas (≥ 2)
Shagreen patch	Retinal achromic patch
Multiple retinal hamartomas	Multiple renal cysts
Multiple cortical tubers and/or radial migration lines	Nonrenal hamartomas
Subependymal nodules (≥ 2)	Sclerotic bone lesions
Subependymal giant cell astrocytoma	
Cardiac rhabdomyoma	
Lymphangioleiomyomatosis (LAM)*	
Angiomyolipomas (≥ 2)*	

* A combination of the 2 major clinical features (LAM and angiomyolipomas) without other features does not meet criteria for a definite diagnosis.

The investigator must document which of the features (major or minor) fulfill the clinical diagnostic criteria.

2. Male or female participants aged 1 through 65 years, inclusive. For Europe (EU), Middle East and North Africa (MENA), and Oceania (OC) Male or Female participants aged 2 through 65 years, inclusive.
3. Participant/parent(s) or LAR(s) willing and able to give written informed consent/assent, after being properly informed of the nature and risks of the study and prior to engaging in any study-related procedures. If the participant is not qualified nor able to provide written informed consent based on age, developmental stage, intellectual capacity, or other factors, parent(s)/LAR(s) must provide consent for study participation, if appropriate.

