8.2.7 Pediatric Quality of Life Inventory - Family Impact Module

Peds-QL-FIM is designed to measure the impact of pediatric chronic health conditions on parents and the family. The Peds-QL-FIM measures parent self-reported physical, emotional, social, and cognitive functioning, communication, and worry. The module also measures parent-reported family daily activities and family relationships (see [Section 10.14](#)).

The Peds-QL-FIM will be conducted at Visit 2 (baseline), Visit 8 (Week 5), Visit 9 (Week 9), and Visit 12 (Week 16). Peds-QL-FIM for past 1 month will be conducted at baseline visit and Peds-QL-FIM for past 7 days will be conducted at on-study visits (see [Section 10.14](#)).

Participants who continue in the OLE will also have the Peds-QL-FIM conducted at Visit 15 (Week 18) and Visit 17 (Week 20).

8.2.8 Short Form 36

The SF-36 is a multi-purpose survey designed to capture participant or parent(s)/caregiver(s)/LAR(s) perceptions of own health and well-being. The SF-36 has 36 items grouped in 8 dimensions: physical functioning, physical and emotional limitations, social functioning, bodily pain, general, and mental health. Version 2 of SF-36 will be used for this study (see [Section 10.15](#)).

The SF-36 will be conducted at Visit 2 (baseline), Visit 4 (Week 1), Visit 8 (Week 5), Visit 9 (Week 9), and Visit 12 (Week 16).

Participants who continue in the OLE will also have the SF-36 conducted at Visit 15 (Week 18) and Visit 17 (Week 20).

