10.15 Appendix 15: Short Form 36 (version 2)

Your Health and Well-Being

This survey asks for your views about your health. This information will help keep track of how you feel and how well you are able to do your usual activities. Thank you for completing this survey!

For each of the following questions, please mark an in the one box that best describes your answer.

1. In general, would you say your health is:

Excellent	Very good	Good	Fair	Poor
				
1	2	3	4	5

2. Compared to one year ago, how would you rate your health in general now?

Much better now than one year ago	Somewhat better now than one year ago	About the same as one year ago	Somewhat worse now than one year ago	Much worse now than one year ago
				
1	2	3	4	5

3. The following questions are about activities you might do during a typical day. Does your health now limit you in these activities? If so, how much?

	Yes, limited a lot	Yes, limited a little	No, not limited at all
	▼	▼	▼

- a Vigorous activities, such as running, lifting heavy objects, participating in strenuous sports 1 2 3
- b Moderate activities, such as moving a table, pushing a vacuum cleaner, bowling, or playing golf 1 2 3
- c Lifting or carrying groceries 1 2 3
- d Climbing several flights of stairs 1 2 3
- e Climbing one flight of stairs 1 2 3
- f Bending, kneeling, or stooping 1 2 3
- g Walking more than a mile 1 2 3
- h Walking several hundred yards 1 2 3
- i Walking one hundred yards 1 2 3
- j Bathing or dressing yourself 1 2 3

4. During the past 4 weeks, how much of the time have you had any of the following problems with your work or other regular daily activities as a result of your physical health?

	All of the time	Most of the time	Some of the time	A little of the time	None of the time
	▼	▼	▼	▼	▼

[figure not shown]
- a Cut down on the amount of time you spent on work or other activities 1..... 2..... 3..... 4..... 5
- b Accomplished less than you would like 1..... 2..... 3..... 4..... 5
- c Were limited in the kind of work or other activities 1..... 2..... 3..... 4..... 5
- d Had difficulty performing the work or other activities (for example, it took extra effort) 1..... 2..... 3..... 4..... 5

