2.3.2. Key Secondary Efficacy Endpoints

- Percentage change from baseline in 28-day primary endpoint seizure frequency during the maintenance period.
- Number (%) of participants considered treatment responders during the double-blind phase.
- Number (%) of participants considered treatment responders during the maintenance period.
- CGI-I at the last scheduled visit in the double-blind phase.

2.3.3. Secondary Efficacy Endpoints (Behavior/Neuropsychiatric/Quality of life):

- Change from baseline in ADAMS total score and sub-score.
- Change from baseline in quality-of-life scales: Peds-QL-FIM, SF-36, and ELDQOL.

2.3.4. Secondary Efficacy Endpoints (Seizure Control):

- Change from baseline in the percentage of seizure-free days during the double-blind phase, based on primary endpoint seizure type.
- Change from baseline in the percentage of seizure-free days during the maintenance phase, based on primary endpoint seizure type.
- CGI-CSID at the last scheduled visit in the double-blind phase.
- Participants with a $\geq 25\%$ and $\geq 75\%$ reduction from baseline in primary endpoint seizure frequency during the double-blind phase.

- Participants with a $\geq 25\%$, $\geq 50\%$, and $\geq 75\%$ reduction from baseline in primary endpoint seizure frequency during the maintenance period.
- Responder analysis for primary endpoint seizures and all seizures during the double-blind phase using the following response categories: $\leq 0\%$, $\geq 0\%$ to < 25%, $\geq 25\%$ to < 50%, $\geq 50\%$ to < 75%, and $\geq 75\%$ to 100%.
- Percent change in 28-day frequency of all seizures.
- Change from baseline in the percentage of seizure-free days, based on all seizure types.
- Change from baseline in the longest seizure-free interval, based on primary endpoint seizure types and all seizure types.

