4.3.5. Secondary Efficacy Endpoints

Summary statistics including confidence intervals for the treatment differences will be used to summarize the results for the secondary endpoints. Testing, as outlined below, will be used for the secondary endpoints.

Change from baseline in ADAMS total score and sub-score.

The ADAMS (Anxiety, Depression, and Mood Scale) is a rating scale designed to screen for anxiety and depression in individuals with intellectual disability. The 28-question scale is filled out by the parent/caregiver/LAR and is based on the subject's behavior during the past 6 months at the Baseline visit and since the last visit at the subsequent visits. Each of the questions are scored as 0 = Not a problem, 1 = Mild problem, 2 = Moderate problem, or 3 = Severe problem. The questions are grouped into 5 subscales:

Manic/ Hyperactive Behavior	Depressed Mood	Social Avoidance	General Anxiety	Obsessive/ Compulsive Behavior
3.	5.	2.	1.	8.
4.	9.	6.	3.	16.
12.	10.	13.	7.	20.
17.	14.	19.	11.	
22.	18.	21.	15.	
	23.	25.	24.	
	28.	27.	26.	

The subscale totals will be summarized with descriptive statistics of the baseline and post-baseline values and the arithmetic changes from baseline.

Change from baseline in quality-of-life scales: Peds-QL-FIM, SF-36, and ELDQOL.

Peds-QL-FIM

The Peds-QL-FIM is designed to measure the impact of pediatric chronic health conditions on parents and the family. The Peds-QL-FIM measures parent self-reported physical, emotional, social, and cognitive functioning, communication, and worry. The module also measures parent reported family daily activities and family relationships (see Protocol Section 10.14).

Total Score is computed by averaging all 36 items. Parent HRQOL Summary Score is computed by averaging 20 items in Physical, Emotional, Social, and Cognitive Functioning. Family Summary Score is computed by averaging 8 items in Daily Activities and Family Relationships.

SF-36

The SF-36 is a multi-purpose survey designed to capture participant or parent/caregiver perceptions of own health and well-being. The SF-36 has 36 items grouped in 8 dimensions: physical functioning, physical and emotional limitations, vitality, social functioning, bodily pain, general, and mental health (see Protocol Section 10.15).

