Scoring the 36-Item Health Survey is a two-step process. First, precoded numeric values are recoded per the scoring key given in Table 1. Note that all items are scored so that a high score defines a more favorable health state. In addition, each item is scored on a 0 to 100 range so that the lowest and highest possible scores are 0 and 100, respectively. Scores represent the percentage of total possible score achieved. In step 2, items in the same scale are averaged together to create the 8 scale scores. Table 2 lists the items averaged together to create each scale. Items that are left blank (missing data) are not taken into account when calculating the scale scores. Hence, scale scores represent the average for all items in the scale that the respondent answered.

Table 1: Recoding Items for SF-36

Item numbers	Change original	To recoded
	response category	value of:
1, 2, 20, 22, 34, 36	1 →	100
	2 ->	75
	3 →	50
	4 →	25
	5 →	0
3, 4, 5, 6, 7, 8, 9, 10, 11, 12	1 →	0
	$2 \rightarrow$	50
	3 →	100
13, 14, 15, 16, 17, 18, 19	1 ->	0
	$2 \rightarrow$	100
21, 23, 26, 27, 30	1 →	100
	2 ->	80
	3 →	60
	4 →	40
	5 →	20
	6 →	0
24, 25, 28, 29, 31	1 →	0
	2 ->	20
	3 →	40
	4 →	60
	5 →	80
	6 →	100

Item numbers	Change original response category	To recoded value of:
32, 33, 35	1 →	0
	$2 \rightarrow$	25
	3 →	50
	4 →	75
	5 →	100

Table 2: Averaging Items to Form Scales for SF-36

Scale	Number of items	After recoding per Table 1, average the following items
Physical functioning	10	3 4 5 6 7 8 9 10 11 12
Role limitations due to physical health	4	13 14 15 16
Role limitations due to emotional problems	3	17 18 19
Energy/fatigue	4	23 27 29 31
Emotional well-being	5	24 25 26 28 30
Social functioning	2	20 32
Pain	2	21 22
General health	5	1 33 34 35 36

ELDQOL

The ELDQOL is a 70-item parent/caregiver-reported measure that examines seizure severity, seizure related injury, AED side effects, behavior, mood, physical status, cognitive and social functioning, communication, overall health and quality of life, and family concerns. The higher the score, the poorer the participant's quality of life (see Protocol Section 10.16). See the scoring instructions below:

Scoring instructions for 4 subscales of the re-validated version of ELDQOL

Seizure Severity Scale (Qs. 1 – 14)

Qs. 1, 5, 7, 8, 9, 10, 11, 13

Reverse the individual item scoring so that

- 1 = 4
- 2 = 3
- 3 = 2
- 4 = 1
- 5 define as a missing value so that it is not included in the calculation of the scale score

Qs. 4, 12

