Reverse the individual item scoring so that

- 1 = 4
- 2 = 3
- 3 = 2
- 4 = 1
- 5 = 0
- 6 define as a missing value

Qs. 2, 14

5 - Define 5 as a missing value. Other scores unchanged.

Qs. 3, 6

5 = 0

Define 6 as a missing value.

Other scores unchanged

Total scale score range = 10-56

Side-effects Profile (Qs. 17 & 18) (Only items in Q.18 used to compute sub-scale.)

Score is the sum of the individual scores for each of the 19 items in Q.18

For each item, score of 5 - define as a missing value.

Any additional problems itemised by respondents should be recorded, but are not added to the total scale score.

Total scale score range = 19-76, where high scores = high level of side effects reported.

Behaviour (Qs. 19 - 27)

Qs.19, 24, 25, 26

Define 5 as a missing value Other scores unchanged

Qs. 20, 21, 27

Reverse scoring so that:

1 = 4

2 = 3

3 = 2

4 = 1

5 - define as a missing value

Qs.22, 23

Recode so that:

5 = 4

6 – define as a missing value Other scores unchanged

Total scale score range = 9-36

Mood Scale (Q. 28)

Reverse scoring of negative items (aggressive, irritable, tearful, hyperactive, sad, agitated, restless, tantrum-prone, frustrated, withdrawn), so that:

1 = 4

2 = 3

3 = 2

4 = 1

5 - define as a missing value

Total Scale score range = 16-64

General points

For each subscale, higher score = poorer QOL / functioning.

Give non-responses a missing value (suggest 9 or -9).

The mean score for each subscale is computed as the sum of the items divided by the number of items answered. To take account of any missing data in a subscale, the mean of the completed items can be imputed, providing at least 50% of the items are completed. If more than 50% of the items in the subscale are missing, then the total subscale score should be classed as a missing value.

All scales and subscales will be summarized separately with descriptive statistics of the baseline and post-baseline values and the arithmetic changes from baseline.

Change from baseline in the percentage of seizure-free days during the DB phase, based on primary endpoint seizure type.

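### Each SF-36 scale mixes participants' ratings of their own health with caregivers' ratings of theirs, so its treatment difference cannot be read as either

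*SAP*

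**What the plan says.** **Who answers, and about whom.** SAP 4.3.5 presents the SF-36 as "designed to capture participant or parent/caregiver perceptions of own health and well-being". Protocol 8.2.8 has the same rule with the LAR added: the participant, or "parent(s)/caregiver(s)/LAR(s) perceptions of own health and well-being". The form in Protocol Appendix 15 opens "This survey asks for your views about your health" and has no proxy wording.

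**Who is in the trial.** Protocol 5.1, criterion 2: "Male or female participants aged 1 through 65 years, inclusive" (2 through 65 in EU, MENA and OC). Criterion 3 foresees participants who cannot consent because of age, development or intellectual capacity. Both kinds of respondent are therefore to be expected.

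**What is done with the answers.** The SAP lists "Change from baseline in quality-of-life scales: Peds-QL-FIM, SF-36, and ELDQOL" among its secondary efficacy endpoints. Under SAP 4.3.5 one scoring key serves every form, and "scale scores represent the average for all items in the scale that the respondent answered". The summary rule is: "All scales and subscales will be summarized separately with descriptive statistics of the baseline and post-baseline values and the arithmetic changes from baseline". That separates scales, not respondents. The section opens by promising confidence intervals for treatment differences on the secondary endpoints, and SAP 3.3 gives non-key secondary endpoints an unadjusted two-sided 5% alpha.

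**The concern.** Two stated rules combine badly. One lets either of two people describe their own health. The other averages whatever was recorded, by scale and by arm. A toddler's record then holds a parent's stairs, pain and mood, while an able adult's record holds the participant's. Both enter the same mean change.

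At stake is whether a listed secondary endpoint, serving the stated objective on mood, behavior and quality of life, can support any statement. A favourable SF-36 difference could not be attributed to participants or to caregivers, and a null one could hide an effect in either group.

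**Working it through.** **1. Compare the instruments.** The other caregiver-facing instruments say who responds or record it:

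| Instrument | Respondent |
|---|---|
| ADAMS (Protocol 8.2.6) | parent/caregiver/LAR, about the participant |
| Peds-QL-FIM (Schedule of Activities footnote; 8.2.7) | parent/caregiver/LAR, about self and family |
| ELDQOL (8.2.9; Appendix 16) | parent/caregiver/LAR, about the participant; the form asks the relationship |
| CGI-I, CGI-CSID (Appendices 10, 11) | forms carry rater initials |
| SF-36 (8.2.8; Appendix 15) | participant or parent/caregiver/LAR, each about self; no schedule footnote, and no respondent field on the form as reproduced |

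**2. Look for a separating rule.** SAP 4.3.5 has no respondent variable or split. The subgroups in SAP 4.3.7 apply to the primary endpoint only and do not include respondent. Mixing follows from this absence; no sentence orders it.

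**3. Plan figures.** The documents give no SF-36 effect, SD or caregiver share. Their only power figure is for the primary endpoint (64 per arm, difference 25, SD 43). By the normal approximation z = 25 / (43 × √(2/64)) = 3.29, and power = Φ(3.29 - 1.96) = 0.908. It reproduces the stated 90% and has no bearing on the SF-36.

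**4. What the pooled difference estimates.** Let p be the share of caregiver forms (equal in both arms in expectation), d the treatment effect on participants' own health, and cd the effect on caregivers' own health. Then

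pooled effect = (1 - p)d + p·c·d = (1 - p + cp)d.

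Both p and c are assumptions:

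| p | c = 0 | c = 0.5 | c = 1 |
|---|---|---|---|
| 0% | 1.00d | 1.00d | 1.00d |
| 25% | 0.75d | 0.875d | 1.00d |
| 50% | 0.50d | 0.75d | 1.00d |
| 75% | 0.25d | 0.625d | 1.00d |
| 90% | 0.10d | 0.55d | 1.00d |

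**5. Power, as illustration only.** Assume d = 0.5 SD, unit SD of change in both respondent types, 64 per arm and two-sided 5%. The mixture adds p(1 - p)((1 - c)d)² to the variance in the GNX arm. For p = 50%, c = 0: the effect is 0.25; the GNX variance is 1 + 0.25 × 0.25 = 1.0625; the pooled SD is √((1 + 1.0625)/2) = 1.016; z = 0.25 / (1.016 × √(2/64)) = 1.39; power = Φ(1.39 - 1.96) = 29%. Likewise:

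| p | 0% | 25% | 50% | 75% |
|---|---|---|---|---|
| c = 0 | 81% | 55% | 29% | 10% |
| c = 0.5 | 81% | 69% | 56% | 42% |

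Both the size and the meaning of the estimate depend on a respondent mix that the plan does not control.

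**The case against.** - **Pooling is inferred from silence.** The SAP rests on CRFs approved on 20APR2023, and Protocol 10.1.8 refers to eCRF completion guidelines. Neither is among the documents, and either may record the respondent or tell sites who should answer. This stands as a limit. Even if respondent type is captured, the SAP's summary does not use it.
- **Caregiver health may be an intended target.** The SF-36 is listed beside the Peds-QL-FIM, a parent and family measure, and the plan never calls it a participant endpoint. This also stands, and it means a reader should not describe the problem simply as a diluted patient effect. It does not rescue the pooled figure, which is no cleaner as a caregiver outcome.
- **It may be meant as proxy rating.** The wording and the form point the other way. Under that reading self-report and proxy report would still be mixed.
- **Randomisation protects the comparison.** Respondent mix is balanced between arms in expectation, and under blinding a change of respondent should mainly add noise. This is correct: the problem is interpretability more than bias between arms. A same-person rule is also missing for the other caregiver instruments.
- **Little depends on it.** The SF-36 is non-key, the Schedule of Activities places it under exploratory assessments, no specific test is outlined for it, and ELDQOL covers participant quality of life separately. This limits the consequence but does not make the planned estimate readable.

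**Conclusion.** The point holds. As written, each of the eight SF-36 scale differences combines participants' health with caregivers' health and cannot be read as either. The size is unknown and follows (1 - p + cp)d: at p = 50%, 0.5d for c = 0 and 0.75d for c = 0.5. Neither p nor c is in the documents. No primary, key secondary or safety conclusion changes.

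Four stronger readings are tempting and are not supported:

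- That the SAP forms one overall SF-36 score. It forms eight, and the mixing occurs within each.
- That the analysis would show only 50% down to 10% of a true patient effect. That needs an assumed caregiver share of 50% to 90% and no effect at all on caregivers' own health. With c = 0.5 the same shares give 75% down to 55%.
- That respondents will switch between visits and bias the result. With five administrations from baseline to Week 16 a switch is possible, and that record's change would then compare two people. Nothing in the documents shows that it happens or how often.
- That records with a changed respondent should be dropped. That would exclude randomised participants for a post-randomisation event, which could itself introduce bias.

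**What to change.** **SAP 4.3.5.** Summarise the SF-36 in two sets of tables, participant self-report and caregiver own health, classified by who answered at Visit 2. If that form is completed before the first dose, the classification is a baseline one and keeps the randomised comparison within each set. Where the respondent later changed, flag and list the record, and show results with and without it as a sensitivity summary.

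**Protocol 8.2.8.** State that the same respondent should answer at every visit, and record who answered each time.

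**Cost.** SAP and protocol wording, one table split and, if not already captured, one respondent field on the eCRF. Each table will have a smaller n. If respondent type was not captured, it may not be recoverable for visits already completed, and the split would then be incomplete. The primary endpoint and the alpha allocation are untouched.

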5. During the past 4 weeks, how much of the time have you had any of the following problems with your work or other regular daily activities as a result of any emotional problems (such as feeling depressed or anxious)?

[figure not shown]
	All of the time	Most of the time	Some of the time	A little of the time	None of the time
	▼	▼	▼	▼	▼

- a Cut down on the amount of time you spent on work or other activities 1..... 2..... 3..... 4..... 5
- b Accomplished less than you would like 1..... 2..... 3..... 4..... 5
- c Did work or other activities less carefully than usual 1..... 2..... 3..... 4..... 5

[figure not shown]
6. During the past 4 weeks, to what extent has your physical health or emotional problems interfered with your normal social activities with family, friends, neighbors, or groups?

7. How much bodily pain have you had during the past 4 weeks?

8. During the past 4 weeks, how much did pain interfere with your normal work (including both work outside the home and housework)?

9. These questions are about how you feel and how things have been with you during the past 4 weeks. For each question, please give the one answer that comes closest to the way you have been feeling. How much of the time during the past 4 weeks.

	All of the time	Most of the time	Some of the time	A little of the time	None of the time
a Did you feel full of life?	 1.....	 2.....	 3.....	 4.....	 5.....
b Have you been very nervous?.....	 1.....	 2.....	 3.....	 4.....	 5.....
c Have you felt so down in the dumps that nothing could cheer you up?.....	 1.....	 2.....	 3.....	 4.....	 5.....
d Have you felt calm and peaceful?.....	 1.....	 2.....	 3.....	 4.....	 5.....
e Did you have a lot of energy?.....	 1.....	 2.....	 3.....	 4.....	 5.....

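### SAP Table 1 applies two-level and six-level keys to SF-36 items that have five responses on the protocol's version 2 form, so four of the eight scales are mis-scored

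*SAP*

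**What the plan says.** Protocol Section 8.2.8 states the version: "Version 2 of SF-36 will be used for this study". Appendix 15 (Section 10.15) prints the form. Question 4, parts a to d, and question 5, parts a to c, ask how often the respondent was limited. Each has five columns coded 1 to 5, as in "Accomplished less than you would like 1..... 2..... 3..... 4..... 5" and "Did work or other activities less carefully than usual 1..... 2..... 3..... 4..... 5". Question 9 ("These questions are about how you feel and how things have been with you during the past 4 weeks") has nine parts under the same five headings.

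SAP Section 4.3.5 cites protocol Section 10.15 as the instrument. Its Table 1 then sets these keys:

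- Items "13, 14, 15, 16, 17, 18, 19": 1 scores 0 and 2 scores 100. No other response is keyed.
- Items 21, 23, 26, 27, 30: responses 1 to 6 score 100, 80, 60, 40, 20, 0.
- Items 24, 25, 28, 29, 31: responses 1 to 6 score 0, 20, 40, 60, 80, 100.

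The same section says that "each item is scored on a 0 to 100 range so that the lowest and highest possible scores are 0 and 100, respectively", with high scores favourable, and that "items in the same scale are averaged together to create the 8 scale scores". Table 2 lists the items in each scale. Blank items are left out of the average. Change from baseline in SF-36 is a secondary endpoint in SAP Section 2.3.3.

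**The concern.** The scoring key and the form do not have the same number of responses. A key with too few levels leaves valid answers without a score and puts the others in the wrong place. A key with too many levels means one end of the range can never be reached.

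On the two role scales the unscored answers are the better ones. A participant who becomes less limited moves out of the scored range, so whether a score exists depends on the outcome itself. That can bias a treatment comparison. The programmer would also have to decide what to do with codes 3, 4 and 5. The SAP's rule covers blank items only, and these items are answered. A choice made after unblinding would not be pre-specified.

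**Working it through.** **Mapping.** Numbering the form's questions in order gives Q1 and Q2 = items 1 and 2, Q3a-j = 3 to 12, Q4a-d = 13 to 16, Q5a-c = 17 to 19, Q6 to Q8 = 20 to 22, Q9a-i = 23 to 31, Q10 = 32, Q11a-d = 33 to 36. This numbering is inferred by counting, and it agrees with the scale names and item counts in SAP Table 2.

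**The SAP's own figure.** Table 1 covers all 36 items once each. Taken alone it does give 0 to 100 on all eight scales, but only if items 13 to 19 have two responses and items 23 to 31 have six.

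**Count of mismatches.** 7 items (13 to 19) + 9 items (23 to 31) = 16 of 36. By Table 2 they form all of role-physical (13 to 16), role-emotional (17 to 19), energy/fatigue (23, 27, 29, 31) and emotional well-being (24, 25, 26, 28, 30): 4 of 8 scales.

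**Comparison key.** Five equally spaced levels: 0, 25, 50, 75, 100 for items 13 to 19, 24, 25, 28, 29 and 31; 100, 75, 50, 25, 0 for items 23, 26, 27 and 30. The SAP already uses 0, 25, 50, 75, 100 for item 32 (Q10), which has the same 'All of the time' to 'None of the time' responses.

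**Role-physical**, with unkeyed codes treated as missing:

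| Responses to Q4a-d | SAP key | Five-level key |
|---|---|---|
| 1, 1, 1, 1 | 0 | 0 |
| 2, 2, 2, 2 | 100 | 25 |
| 3, 3, 3, 3 | no score | 50 |
| 4, 4, 4, 4 | no score | 75 |
| 5, 5, 5, 5 | no score | 100 |
| 1, 5, 5, 5 | 0/1 = 0 | (0 + 3 × 100)/4 = 75 |
| 2, 5, 5, 5 | 100/1 = 100 | (25 + 3 × 100)/4 = 81.25 |

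A participant who improves from 'Most of the time' to 'None of the time' on every item goes from 100 to no score. The five-level key gives 25 to 100, a gain of 75. Role-emotional uses the same key and fails in the same way.

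**Energy/fatigue and emotional well-being.** Let F be an item's five-level score. On a negatively worded item, response r scores 20(r − 1) under the SAP and F = 25(r − 1), so the SAP score is 0.8F. On a positively worded item the SAP score is 100 − 20(r − 1) and F = 100 − 25(r − 1), so the SAP score is 20 + 0.8F. Averaging over complete responses:

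- Energy/fatigue has two positive items of four: (2 × 20)/4 + 0.8F = 10 + 0.8F. Best = (100 + 100 + 80 + 80)/4 = 90; worst = (20 + 20 + 0 + 0)/4 = 10.
- Emotional well-being has two positive items of five: (2 × 20)/5 + 0.8F = 8 + 0.8F. Best = (3 × 80 + 2 × 100)/5 = 88; worst = (3 × 0 + 2 × 20)/5 = 8.

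In these two averages F is the scale's five-level score. Both relations were confirmed over every possible response pattern. Each change from baseline, and each treatment difference, is multiplied by 0.8.

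**After the change.** With the five-level keys all four scales again run from 0 to 100.

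**The case against.** No passage removes the mismatch. The arguments on the other side concern how much it matters and how it should be described.

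- **Rank of the endpoint.** SF-36 is a non-key secondary endpoint outside the gatekeeping sequence, and Section 4.3.5 sets out only descriptive statistics for it. This stands: no primary, key secondary, safety or sample-size result depends on Table 1. But Section 4.3.5 also promises confidence intervals for treatment differences on secondary endpoints, and Section 3.3 allows unadjusted 5% testing, so the scores will be used for comparison.
- **The two pairs of scales fail differently.** This also stands. For complete responses, energy/fatigue and emotional well-being are a linear compression; rank order and between-group p-values do not change. Only the role scales lose answers and misplace others.
- **'Missing' is one reading.** The SAP does not say what happens to an answered item whose code is not in the key, and a programmer would probably notice. That is fair. It means the rule is incomplete, not that it works.
- **Not everything in version 2 is five-level.** Q3 has three levels and matches the SAP. The response options for Q6 to Q8 are not legible in the text reviewed, including "How much bodily pain have you had during the past 4 weeks" (item 21), so no error is claimed for items 20 to 22.
- **The documents give no version 2 key.** The five-level spacing here extends what the SAP does for item 32. It is a reasonable choice, but it should be checked against the instrument's scoring instructions.

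**Conclusion.** The concern holds. Sixteen of 36 items, and four of eight SF-36 scales, are scored with a key that does not fit the form the protocol prints, against the SAP's own 0 to 100 rule.

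The serious part is role-physical and role-emotional. Three of five answers have no score, 'Most of the time' limited receives the best score, and the least limited participants are the ones lost. As written, a stated secondary endpoint cannot be validly computed on these scales. The other two scales are correctly ordered but 20% too small in every change and treatment difference.

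This rests on two assumptions: that the case report form records the codes 1 to 5 printed in Appendix 15, and that items are numbered in form order. The 'no score' entries for whole role scales also assume that unkeyed answers are treated as missing. The confirmatory tests are not affected.

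**What to change.** Amend SAP Table 1 before database lock and unblinding:

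- Items 13 to 19 and 24, 25, 28, 29, 31: 1 = 0, 2 = 25, 3 = 50, 4 = 75, 5 = 100.
- Items 23, 26, 27, 30: 1 = 100, 2 = 75, 3 = 50, 4 = 25, 5 = 0.
- Item 21: keep the six-level key only if the full form shows six responses. Check items 20 and 22 against the form at the same time.

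Confirm these keys against the version 2 scoring instructions, state how an answered item with an out-of-range code is handled, and record the change in SAP Section 8. The cost is one table correction and reprogramming of the SF-36 derivation. No data need to be collected or changed.
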